4.2 Mock Graphs

Figure 1. Study Patient Screening and Enrollment

[figure not shown]

Figure 2. FLU-PRO Symptom Severity Score for Enrolled Patients, by Domain of Symptoms, up to 14 Days from Enrollment

Figure 3. Karnofsky Performance Scale, Mean and 95% Confidence Band of Daily Scores

Figure 4. Severity of Disease for Hospitalized Patients, up to 14 Days from Enrollment

Figure 5. Ordinal Scale for Hospitalized Patients, up to 14 Days from Enrollment

4.3 *Mock Listings*

Listing 1. Patient Level Adverse Events

Patient Identifier	Site	Study Arm	Start Date	Resolution Date	AE Code (MedDRA, CTCAE)	Severity	SAE? (Y/N)	Relatedness	Hospitalization Type	Outcome	Comments

Severity of AE:

- 1 = Mild
- 2 = Moderate
- 3 = Severe
- 4 = Potentially Life threatening or disabling
- 5 = Death

Outcome:

- 1 = Ongoing
- 2 = Resolved without sequelae
- 3 = Resolved with sequelae
- 4 = Death**
- 5 = Worsened
- 6 = Chronic
- 7 = Lost to follow-up

Relatedness to Study Drug:

- 0 = Not related
- 1 = Related

Hospitalization:

- 0 = None
- 1 = ICU
- 2 = Step down unit
- 3 = Other

**Provide further details regarding all reported serious AEs and deaths in the SAE and Subject Deaths tables listed at the end of this section.

Listing 2. Serious Adverse Events

Patient Identifier	Site	Study Arm	SAE Onset Date	Outcome Date	Outcome	SAE Classification	Severity	Related to Study Drug	Description of Actions and Outcomes (e.g. hospitalization, withdrawn from study)

Severity of SAE:

1 = Mild
2 = Moderate
3 = Severe
4 = Life threatening or disabling
5 = Death

SAE Classification:

1 = Death
2 = Life threatening
3 = Inpatient hospitalization or prolonged hospitalization
4 = Persistent/significant disability/incapacity
5 = Resulted in congenital anomaly/birth defect
6 = Important medical event

Relatedness to Intervention:

0 = Not related
1 = Related

Outcome:

1 = Ongoing
2 = Resolved without sequelae
3 = Resolved with sequelae
4 = Death**
5 = Worsened
6 = Chronic
7 = Lost to follow-up

Listing 3. Deaths

Patient Identifier	Site	Study Arm	Age	Date Enrolled	Treatment Date	Cause of Death	Date of Death	Comments

Table of Contents

Sponsor and Principal Investigator Signatures.....	5
List of Abbreviations.....	6
Protocol Summary.....	8
Schematic of Study Design.....	10
1. Background	11
1.1. Scientific Rationale.....	11
1.2. Potential Risks and Benefits.....	11
1.2.1. Potential Risks	12
1.2.2. Potential Benefits.....	14
2. Objectives.....	14
2.1. Study Objectives.....	14

SMC	Safety Monitoring Committee
SOP	Standard Operating Procedure
TAT	Turnaround Time
US	United States

Protocol Summary

Title:	A Pilot Randomized Controlled Trial for Feasibility of Enrolling Subjects for Influenza Therapeutic Trials and Administering Influenza Antivirals in the Emergency Department to High Risk Subjects
Population:	Adults presenting to the emergency department (ED) with laboratory-confirmed influenza who meet Centers for Disease Control and Prevention (CDC) criteria for antiviral treatment
Informed Consent:	Written informed consent
Number of Sites:	2 – large, urban, academically-affiliated, US EDs
Study Duration:	September 2015 – September 2018
Subject Participation Duration:	4 weeks
Description of Agent or Intervention:	Subjects will be randomized to either oral (oseltamivir) or intravenous (IV) (peramivir) antiviral treatment.
Objectives:	
This pilot study is designed to demonstrate the feasibility of utilizing EDs as a primary site for subject enrollment in clinical trials evaluating influenza therapeutics, providing pilot data for future clinical trial design and planning.
 
Primary Objective: To prospectively enroll high-risk subjects with laboratory-confirmed influenza into a randomized, open-label study of oral versus IV influenza therapeutic to include symptom evaluation and outcome assessments.
 
Secondary Objective 1: To identify influenza-positive patients utilizing a previously established triage-based assessment and rapid testing algorithm for suspected influenza infection.
 
Secondary Objective 2: To retrospectively evaluate all potentially eligible patients for potential enrollment biases.
 
Secondary Objective 3: To create a repository of residual nasopharyngeal (NP) samples collected from ED patients with suspected influenza illness.

Description of Study Design:	This is an open-label randomized controlled clinical trial in which subjects with influenza are randomized to either oral (oseltamivir) or IV (peramivir) antiviral treatment.

Estimated Time to Complete Enrollment: Subject enrollment will occur over two influenza seasons (November 2015 – April 2017) or longer, at the co-principal investigators' (Co-PIs') discretion, based on influenza prevalence.

Schematic of Study Design

1. Background

1.1. Scientific Rationale

Although new influenza therapeutics are needed to mediate population level morbidity and mortality associated with both seasonal and pandemic influenza, clinical trials evaluating emerging therapeutics have been challenging. One well-recognized challenge with prior large trials is that they historically have recruited otherwise healthy subjects at clinical sites with relatively low rates of recruitment, resulting in the need to engage up to hundreds of recruitment sites, and a relative lack of patients with more severe and/or complicated illness. This has introduced management challenges with trial implementation and evaluation, including high associated costs for subject recruitment and retention.

As the first line of care for many patients with influenza, and over 130 million visits/year, US emergency departments (EDs) represent an as yet untapped clinical venue for recruiting individuals with influenza into clinical trials. Notably, EDs also have the advantage of caring for patients early in their clinical course, and frequently serve as the initial site of care for those with complicated and/or severe influenza. Taken together, this creates opportunities which could be leveraged for design and implementation of more streamlined influenza therapeutic clinical trial design. We propose a pilot study to demonstrate the feasibility of utilizing EDs as primary sites for subject enrollment in clinical trials evaluating influenza therapeutics, providing data to inform future clinical trial design and planning.

1.2. Potential Risks and Benefits

The risks and benefits for subjects enrolled in this trial are appropriately balanced. All of the study interventions are consistent with recommended clinical practice. The triage algorithm for influenza testing is a standard operating procedure (SOP) in the ED from November through April. The drugs under study (i.e., oseltamivir and peramivir) have both been approved by the US Food and Drug Administration (FDA) for the treatment of acute uncomplicated influenza in patients 18 years and older who have been symptomatic for no more than two days.

Additionally, the Centers for Disease Control and Prevention (CDC), Infectious Diseases Society of America, and the World Health Organization recommend antiviral treatment with a neuraminidase inhibitor as soon as possible for all persons with suspected or confirmed influenza who are at higher risk for influenza complications, or who have severe or complicated illness. These recommendations come from multiple observational studies showing reduction in morbidity and mortality. The strongest evidence remains in hospitalized patients, where both early initiation of antiviral treatment (less than two days from illness onset) and treatment up to five days after symptom onset were associated with reduced mortality, with greater benefit associated with earlier initiation of treatment. All subjects in this study will be adults at higher risk for influenza, who are recommended to receive antiviral treatment in accordance with CDC recommendations. Many of these subjects may require hospitalization for disease severity and/or underlying conditions. [<http://www.cdc.gov/flu/professionals/antivirals/antiviral-use-influenza.htm>]

1.2.1. Potential Risks

The risks to subjects enrolled in the study will be comparable to those encountered by similar patients receiving standard care. These risks include minor risks associated with study participation and adverse events (AEs), including reactions to the study drugs (see below).

Subjects will be carefully screened to ensure that they meet all study inclusion criteria and do not have any exclusion criteria that would put them at unnecessary risk from study participation. Subjects will be contacted for follow-up at Day 28, and will have access 24 hours a day, 7 days a week, to on-call research staff, investigators, and emergency care if questions should arise.

Minor risks associated with study participation include added time associated with completing study questionnaires, pain or discomfort during a blood draw, or unanticipated disclosure of a subject's underlying medical conditions. To minimize these risks and discomforts, trained personnel who have completed all Health Insurance Portability and Accountability Act (HIPAA) training and procedures associated with enrollment of human subjects and study related procedures, will approach, consent, enroll patients, and collect data. Further, trained personnel will only approach patients and conduct study related activities during patients' ED wait times, decreasing risk of potential increased ED care time associated with study related procedures. Baseline laboratory tests and a chest x-ray are non-invasive and standard treatment in the ED, and therefore, pose no additional study-associated risk. To minimize any potential discomfort, trained personnel will collect all specimens.

Subjects will be carefully screened for possible AEs after receiving study drug, and will be provided with information to contact the study team for any possible AE that occurs throughout the trial. Subjects with findings suggestive of possible AEs will have the appropriate investigations performed. Serious adverse events (SAEs) will be defined *a priori*, and reported to the independent safety monitor (ISM) and the Institutional Review Board (IRB) as described in section 8; subjects will be advised and provided with referral sites to seek medical treatment.

The study will be conducted in accordance with Good Clinical Practice (GCP), and full compliance with 21 Code of Federal Regulations (CFR) Parts 11, 50, 54, 56, and 312; 45 CFR Part 46 (Protection of Human Subjects); and the HIPAA Privacy Rule. Procedures for managing protected health information (PHI) will be included in the written informed consent form (ICF). Numerous safeguards will be put in place to ensure the confidentiality and integrity of all data, addressing both the human and physical elements of protecting subject confidentiality. These include data management staff training in protection of human subjects and the ethical conduct of human research, systematic backup for the centralized database, use of encrypted data on durable media, and utilization of encryption and role-based access mechanisms for remote access in compliance with industry best practices and consistent with security and privacy requirements of the IRB. Any paper documentation containing PHI, such as informed consent documents, will be stored securely by research staff. See section 11.4 for further information on maintaining confidentiality to reduce PHI disclosure risks.

Depending on the randomization, a subject may receive oseltamivir or peramivir. According to the current package insert, the following warnings and precautions, drug interactions, and AEs are reported with these study drugs:

Oseltamivir (Tamiflu)

Warnings and Precautions:

Serious skin/hypersensitivity reactions such as Stevens-Johnson Syndrome, toxic epidermal necrolysis and erythema multiforme: Discontinue TAMIFLU and initiate appropriate treatment if allergic-like reactions occur or are suspected.

Neuropsychiatric events: Patients with influenza, including those receiving TAMIFLU, particularly pediatric patients, may be at an increased risk of confusion or abnormal behavior early in their illness. Monitor for signs of abnormal behavior.

Drug Interactions:

Live attenuated influenza vaccine (LAIV), intranasal:

Do not administer until 48 hours following cessation of TAMIFLU.

Do not administer TAMIFLU until two weeks following administration of the LAIV, unless medically indicated.

Adverse Reactions:

Most common adverse reactions (>1% and more common than with placebo):

Treatment studies – Nausea, vomiting, bronchitis, insomnia, vertigo.

Prophylaxis studies – Nausea, vomiting, diarrhea, abdominal pain.

Peramivir (Rapivab)

Warnings and Precautions:

Serious skin/hypersensitivity reactions such as Stevens-Johnson Syndrome and erythema multiforme have occurred with RAPIVAB.

Neuropsychiatric events: Patients with influenza may be at an increased risk of hallucinations, delirium, and abnormal behavior early in their illness. Monitor for signs of abnormal behavior.

Drug Interactions:

LAIV, intranasal: Avoid use of LAIV within 2 weeks before or 48 hours after administration of RAPIVAB, unless medically indicated.

Adverse Reactions:

Most common adverse reaction (incidence >2%) is diarrhea.

This study is only enrolling subjects with confirmed influenza who are recommended to receive antiviral treatment according to current CDC guidelines, and treating them with appropriate

antiviral drugs which have been FDA approved to treat patients with influenza. The most commonly used antiviral treatment for influenza is oseltamivir, which is recommended by the CDC antiviral treatment guidelines. Oseltamivir has a low side effect profile, and has been shown to reduce the duration of symptoms in randomized control trials with outpatients and is approved by the FDA for treatment of uncomplicated influenza within 48 hours of symptom onset. Observational studies have shown that oseltamivir reduces mortality, hospital length of stay, and influenza-related complications in various high-risk groups. Peramivir, which is in the same neuraminidase inhibitor class as oseltamivir but is delivered in an intravenous (IV) formulation, has likewise been approved by the FDA for treatment of uncomplicated influenza within 48 hours of symptom onset. Peramivir also has a low side effect profile. There are insufficient studies to date, regarding the use of peramivir for hospitalized patients with influenza.

1.2.2. Potential Benefits

All of the study interventions are standard of care for patients with influenza, and both of the drugs under study are currently FDA approved and used for the treatment of acute uncomplicated influenza.

Subjects will receive study drugs free of charge. Additionally, subjects will have more intensive follow-up than would be routinely provided for ED patients in these facilities, and therefore, any potential complications or treatment failure will be addressed more promptly than standard of care might otherwise allow. Further, an independent, on-call infectious diseases specialist will be made available as part of the study procedures to provide real time consultation to clinicians caring for subjects participating in the study, which may provide additional benefit to subjects participating in the study. Finally, participation in this study will help inform future studies of influenza treatment, which could help in developing improved treatment for future patients with influenza.

2. Objectives

2.1. Study Objectives

Primary Objective: To prospectively enroll high-risk subjects with laboratory-confirmed influenza into a randomized, open-label study of oral versus IV influenza therapeutic to include symptom evaluation and outcome assessments.

Secondary Objective 1: To identify influenza-positive patients utilizing a previously established triage-based assessment and rapid testing algorithm for suspected influenza infection.

Secondary Objective 2: To retrospectively evaluate all potentially eligible patients for potential enrollment biases.

Secondary Objective 3: To create a repository of residual nasopharyngeal (NP) samples collected from ED patients with suspected influenza illness.

2.2. Study Outcome Measures

Primary Objective: To prospectively enroll high-risk subjects with laboratory-confirmed influenza into a randomized, open-label study of oral versus IV influenza therapeutic to include symptom evaluation and outcome assessments.

Outcomes: The number of subjects successfully enrolled; the proportion of subjects who complete treatment with IV or oral study drug in the ED; the proportion of subjects who complete follow-up.

In addition, the following clinical measures will be evaluated for planning future clinical trial endpoints:

- For all subjects:
 - Reported symptoms (including FLU-PRO Symptom Questionnaire);
 - Daily functional assessment;
 - Patient Global Impression of Change (PGIC) on Day 7 and Day 28;
 - Patient Global Impression of Severity (PGIS) at enrollment, and on Day 7 and Day 28;
 - Number of subsequent medical visits or hospitalizations within 28 days of enrollment; and
 - Influenza-related complications including pneumonia, myocardial infarction, and stroke.
- For subjects initially admitted to the hospital from the ED:
 - Severity of disease based on Intensive Care Unit (ICU) admission, mechanical ventilation, or oxygen supplementation; and
 - Ordinal scale up to 14 days:
 - Death;
 - Receiving mechanical ventilation or extracorporeal membrane oxygenation (ECMO);
 - In ICU (without mechanical ventilation or ECMO);
 - Non-ICU hospitalization, requiring supplemental oxygen;
 - Non-ICU hospitalization, not requiring supplemental oxygen;
 - Not hospitalized, but unable to resume normal activities; and
 - Not hospitalized with full resumption of normal activities.

Secondary Objective 1: To identify influenza-positive patients utilizing a previously established triage-based assessment and rapid testing algorithm for suspected influenza infection.

Outcomes: The proportion of ED patients who were screened for influenza; the proportion of screened patients who met testing criteria; the proportion of patients who met testing criteria who were tested for influenza; the proportion of patients tested for influenza who were positive for influenza.

Secondary Objective 2: To retrospectively evaluate all potentially eligible patients for potential enrollment biases.

Outcome: The proportion of eligible patients who were enrolled; comparison of demographic characteristics between those who were prospectively enrolled versus not enrolled.

Secondary Objective 3: To create a repository of residual NP samples collected from ED patients with suspected influenza illness.

Outcome: The creation of a robust repository using all remnant samples of patients tested using the triage-based assessment and testing algorithm from November 2015 through April 2017.

3. Systematic Influenza Testing in the Emergency Department

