2.3.1 Outcome Measures and Predictors

Outcomes:

a. For the Primary Objective:

- The number of subjects successfully enrolled
- The proportion of subjects who received treatment with IV study drug in the ED
- The proportion of subjects who received (first dose) oral study drug in the ED
- The proportion of subjects who complete follow-up.

In addition, the following clinical measures will be evaluated for planning future clinical trial endpoints:

- For all study subjects:

- Reported symptoms (including FLU-PRO Symptom Questionnaire)
- Daily functional assessment
- Patient Global Impression of Change (PGIC) on Day 7 and Day 28
- Patient Global Impression of Severity (PGIS) at enrollment, and on Day 7 and Day 28
- Number of subsequent medical visits or hospitalizations within 28 days of enrollment
- Influenza-related complications including pneumonia, myocardial infarction, and stroke.

- For subjects initially admitted to the hospital from the ED:
 - Severity of disease based on Intensive Care Unit (ICU) admission, mechanical ventilation, or oxygen supplementation
 - Ordinal scale up to 14 days:
 - Death
 - Receiving mechanical ventilation or extracorporeal membrane oxygenation (ECMO)
 - In ICU (without mechanical ventilation or ECMO)
 - Non-ICU hospitalization, requiring supplemental oxygen
 - Non-ICU hospitalization, not requiring supplemental oxygen
 - Not hospitalized, but unable to resume normal activities
 - Not hospitalized with full resumption of normal activities.

b. For the Secondary Objective 1:

- The proportion of ED patients who were screened for influenza
- The proportion of screened patients who met testing criteria
- The proportion of patients who met testing criteria who were tested for influenza
- The proportion of patients tested for influenza who were positive for influenza.

c. For the Secondary Objective 2:

- The proportion of eligible patients who were enrolled
- Comparison of demographic characteristics between those who were enrolled in the study versus those who were identified to be potentially eligible through the retrospective chart review.
 - Age
 - Sex
 - Race
 - Ethnicity

d. For the Secondary Objective 3:

- The creation of a robust repository using all remnant samples of patients tested using the triage-based assessment and testing algorithm from November through April 2015 - 2017. Note that this is not a quantitative outcome.

Potential predictors (independent variables) of interest:

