4.1. Retrospective Chart Review

In order to evaluate the full potential ED population who might have met criteria for enrollment, all potentially eligible patients will be evaluated via a retrospective chart review. Basic demographic characteristics of patients who were not approached for enrollment, and those who were approached but not enrolled, will be compared (in a de-identified manner) with those who were enrolled into the Randomized Controlled Trial of Influenza Antivirals.

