4.1.4. Data Collection

For all eligible patients, research staff will review the ED and hospital records to retrospectively complete a set of structured clinical data forms to collect the following: basic demographic data; symptoms related to the CDG; criteria for CDC antiviral treatment; initial presentation and clinical course at the ED, including antiviral treatment, antibiotic treatment, Xpert Flu test or other influenza test information; and hospital course if subsequently admitted.

In accordance with HIPAA regulations, no subject personal identifiers will be entered into the study database. Personal identifiers such as name and medical record number will be collected and recorded on a separate study identification (ID) sheet for purposes of completing the retrospective chart review. This identifying information will be linked to the remainder of the subject information only through the study ID number, and will ultimately be stripped of identifying information after all necessary data and samples are collected. Personal identifiers will be destroyed upon final completion and verification of the study database.

All study documents will be kept locked in a limited access area. The study ID sheet that links the study ID numbers to the subject personal identifiers will be kept under double lock separate from all research files, accessible only to research staff.

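### Secondary Objective 2 compares enrolled and non-enrolled patients on demographics only, so it cannot reliably detect under-enrollment of admitted or sicker patients, although the chart review already abstracts the relevant data

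*Combined protocol and SAP*

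**What the plan says.** **The outcome.** Protocol 2.2 gives Secondary Objective 2 two outcomes: the proportion of eligible patients enrolled, and "comparison of demographic characteristics between those who were prospectively enrolled versus not enrolled". Protocol 4.1 describes the same comparison: "Basic demographic characteristics of patients who were not approached for enrollment, and those who were approached but not enrolled, will be compared" with the enrolled group. SAP 2.3.1 c has "Comparison of demographic characteristics between those who were enrolled in the study versus those who were identified to be potentially eligible" through chart review, followed by four items: age, sex, race and ethnicity. The predictor list in SAP 2.3.1 and the text of SAP 2.4.3 also speak only of demographic characteristics for this contrast.

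**The rationale.** Protocol 1.1 faults earlier large trials for recruiting otherwise healthy subjects and for "a relative lack of patients with more severe and/or complicated illness".

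**The data.** Protocol 4.1.4 has staff abstract demographics, CDG symptoms and the CDC treatment criteria for every chart-review patient. It adds "initial presentation and clinical course at the ED, including antiviral treatment, antibiotic treatment", and "hospital course if subsequently admitted". SAP 1.4.1 repeats the list. No stated outcome uses the clinical fields to compare enrolled with non-enrolled patients.

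**The projection.** Protocol 9.2 and SAP 2.1 expect 174 eligible patients in a routine season and 97 enrolled, of whom 58 are discharged and 39 admitted.

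**The concern.** An objective about enrollment bias should look at the characteristics on which selection is likely and would matter. In this trial severity and disposition are the obvious candidates. The rationale raises them, the recruitment projection is split by disposition, and research staff may approach a patient only with the ED provider's approval (Protocol 4.2.2). That step can filter eligible patients by how ill they are or how they are being managed, and the filtering need not show in age, sex, race or ethnicity.

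At stake is the interpretation of Secondary Objective 2. The trial could report enrolled and non-enrolled patients as demographically alike, and that could be read as absence of enrollment bias, while admitted patients were enrolled at a clearly lower rate. Planners of a later ED-based trial would then lack the figure they need: the fraction of eligible admitted patients that an ED can enroll.

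**Working it through.** **1. Reproduce the projection (Protocol 9.2, SAP 2.1).** Inputs: 311 positives, 75% meeting CDC criteria, 25% fewer positives in a routine season, 56% participation, 40% admitted.

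- Eligible: 311 × 0.75 × 0.75 = 174.9 (stated 174)
- Enrolled: 174 × 0.56 = 97.4 (stated 97)
- Admitted: 97 × 0.40 = 38.8 (stated 39)
- Discharged: 97 × 0.60 = 58.2 (stated 58)

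All four reproduce. The 39 is the overall admitted share applied to the enrolled total. If the same 40% holds among eligible patients, 174 × 0.40 = 70 are admitted and 104 discharged, so enrollment is 39/70 = 56% and 58/104 = 56%. Equal enrollment by disposition is built in.

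**2. Look for a planned check of that assumption.**

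| Place | What it gives | Enrolled vs not enrolled by severity? |
|---|---|---|
| Protocol 2.2, 4.1 | Demographics | No |
| SAP 2.3.1 c | Age, sex, race, ethnicity | No |
| SAP 3.3 | Unspecified subject characteristics; analysis placed outside the SAP | Not defined |
| SAP Tables 5 to 7 | Severity and hospital outcomes by arm | No, enrolled only |
| SAP Table 8 | Counts from ED visit to enrollment | No, not split by disposition |

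**3. What the demographic comparison could pick up (hypothetical).** One routine site-season: 97.4 enrolled and 76.6 not enrolled. Assumptions not in the documents: two-sided alpha 0.05, age SD 18 years, and admitted patients 5, 10 or 15 years older. Overall participation (56%) and admitted share (40%) are held fixed. Suppose 40% of admitted patients enroll.

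- Admitted and enrolled: 69.6 × 0.40 = 27.8
- Discharged and enrolled: 97.4 − 27.8 = 69.6, or 69.6/104.4 = 67%
- Admitted share among enrolled: 27.8/97.4 = 28.6%
- Admitted share among not enrolled: 41.8/76.6 = 54.5%
- Difference: 26.0 points

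*Direct comparison of admission.* Pooled SE = √[0.40 × 0.60 × (1/97.4 + 1/76.6)] = 0.0748. Unpooled SE = √[0.286 × 0.714/97.4 + 0.545 × 0.455/76.6] = 0.0730. Power = Φ[(0.260 − 1.96 × 0.0748)/0.0730] = Φ(1.55), about 94%.

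*Planned comparison of age.* The induced difference is the age gap × 0.260. SE = 18 × √(1/97.4 + 1/76.6) = 2.75 years. Power = Φ(difference/2.75 − 1.96), counting rejections in the true direction.

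| Age gap, admitted minus discharged | Induced difference | Power |
|---|---|---|
| 5 years | 1.3 years | 7% |
| 10 years | 2.6 years | 16% |
| 15 years | 3.9 years | 29% |

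If admission is unrelated to all four listed variables, the planned comparison carries no information about it.

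**4. Precision after the change.** At 97 versus 77 patients and a 40% admitted share, the 95% half-width for the difference in admitted share is 1.96 × √[0.24 × (1/97 + 1/77)] = 0.147, about 15 points. Power reaches 80% at a difference of about 21 points (31% versus 52%). With three such site-seasons (3 × 174 = 522 eligible, assuming the second site has the same yield), it reaches 80% at about 12 points.

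**The case against.** **The enrolled-only tables already describe severity.** SAP Tables 5 to 7 report hospitalization, ICU admission, ventilation, oxygen and the ordinal scale, and the plan expects about 40% admitted. A trial that largely missed admitted patients would look thin in Table 7. This stands as a crude benchmark, but the 40% comes from a prior season at one site. It does not replace a comparison with patients who were not enrolled in the same season.

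**SAP 3.3 speaks of subject characteristics more broadly.** It does, as does the study-site item in SAP 2.3.1. The term is undefined in both places, and SAP 3.3 says the analysis is not part of that SAP. The only explicit list has four demographic items.

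**Most severity-related filters are exclusion criteria.** Inability to consent, inability to take oral medication and recent neuraminidase inhibitor use make patients ineligible, and they do not select among eligible patients. This is correct. Of the filters considered here, only provider approval acts on eligible patients. Reasons for exclusion and refusal are also logged (Protocol 4.2.2), though they are not an outcome of Secondary Objective 2 and do not measure severity.

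**It is a descriptive pilot, and the rows could be added later.** The data would be there. Even so, Protocol 9.3 already plans t-tests or chi-squared tests for this objective, and specifying the variables beforehand avoids choosing them after the results are seen.

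**A stronger reading that fails.** Admission is itself a CDC criterion, so a reader might take 40/75 = 53% of the 174 eligible (93) as admitted and infer enrollment of 39/93 = 42% of admitted against 58/81 = 72% of discharged patients. That mixes a 53% admitted share among eligible patients with a 40% share among enrolled. It also assumes that every admitted positive patient was counted within the 75%, which the documents do not settle. With one share used throughout, the gap disappears.

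**Conclusion.** The point holds as a gap in the stated outcome of Secondary Objective 2. The planned comparison cannot reliably detect under-enrollment of admitted or sicker patients and could not attribute it to severity. The projection's equal enrollment by disposition goes unchecked.

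The size depends on assumptions. Under the hypothetical 40% versus 67% enrollment, power is about 94% for a direct comparison and 7% to 29% for the age comparison. The age SD, the age gap, alpha and the 40% admitted share among eligible patients are illustrative.

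Two inferences go further than the documents allow:

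- *That such bias could never show.* A very large bias closely tied to age could appear indirectly. With 20% versus 80% enrollment and a 15-year age gap, the age comparison has about 89% power, although the cause would remain unidentified.
- *That the main feasibility conclusion would be unsupported.* The primary outcomes in Protocol 2.2 are number enrolled, treatment in the ED and completed follow-up, and none requires a representative severity mix.

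The documents give no evidence that differential enrollment occurs.

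**What to change.** In Protocol 2.2 and 4.1 and SAP 2.3.1 c:

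- Extend the enrolled versus not-enrolled comparison to ED disposition (discharged or admitted), CDC criterion met, presenting symptoms, and antiviral given in the ED.
- Add pneumonia and ICU care where the abstraction form captures them. Protocol 4.1.4 names categories and not every field, so ICU status is only inferred from hospital course and should be checked against the form.
- Report the proportion of eligible patients enrolled within each ED disposition, with confidence intervals. Under the plan's own figures the half-widths would be about 1.96 × √(0.56 × 0.44/70) = 12 points for admitted and 1.96 × √(0.56 × 0.44/104) = 10 points for discharged patients, per routine site-season.
- Show patients not approached and patients approached but not enrolled as separate groups, as Protocol 4.1 already names them.

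The cost is a few more rows in a planned table and little or no new data collection. The downside is a few more unadjusted descriptive comparisons, best read through their confidence intervals.
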